## 4 ANALYSIS SETS

### 4.1 Analysis Set Definitions

The following data sets will be used for the statistical analysis:

**Enrolled (ENR) Set:** all participants who signed an informed consent to participate to the trial

Note: Having signed an informed consent is defined as having a complete date for consent signature in the database.

**Safety (SAF) Set:** All enrolled participants who were randomized and received at least 1 dose, or part thereof, of IMP (ARGX-117 or placebo). Participants will be analyzed according to the treatment they received.

**PK Set:** All participants in the SAF and for whom at least 1 post dose serum PK concentration is available, excluding placebo participants.

**PD Set:** All participants in the SAF for whom at least 1 post-baseline value for PD parameter (including free C2, total C2 and CH50) is available

The SAF set will be used to analyze the primary safety analysis. The SAF will be used to analyze efficacy endpoints.

For analyses performed on the SAF, PK and PD sets, the actual treatment arm will be considered.

[REDACTED]

If a treatment switch or misallocation occurred, sensitivity analyses might be performed.

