## 2.2 Randomization Methodology

In this randomized controlled trial, for each cohort, 24 participants will be randomized using an interactive voice/web response system (IVRS/IWRS).

Participants will be randomized on day 1 of the DBTP:

- In a 2:1 ratio to ARGX-117 or placebo in cohort 1, and for option 1 ( ) or option 2 ( ) in cohort 2
- In a 2:2:1:1 ratio to ARGX-117 ( ) ARGX-117 ( ) placebo ( ) , or placebo ( ) for option 3 in cohort 2

Participants will be randomized on day 1 of the DBTP: ( )

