### 6.3 Study Population

#### 6.3.1 Participant Disposition

Summary data for the ENR set will be presented overall. The denominator for all percentages will be the total number of enrolled participants. Summary data for the SAF set will be presented for each cohort by treatment group and overall.

A tabulation of participant disposition will be presented by treatment group and overall, for enrolled participants, including:

- Number of screened participants
- Number of participants who entered, discontinued the IVDP (including completed IVDP but did not enter IVMP), and who completed IVDP and entered IVMP

- Number of participants who entered, completed and discontinued the IVMP
- Number of screen failures during the screening period, IDVP and IMVP along with the reasons. Screen failures are defined as participants who consent to participate in the clinical trial but are not subsequently randomized to the DBTP. A participant can be screening failure if the participant did not meet protocol criteria at screening visit, IVM1 or V1 or discontinued the study before randomization
- Number of participants randomized

A tabulation of participant disposition will be presented for each cohort by treatment group and overall, for SAF set, including:

- Number of participants who entered, discontinued the IVDP, and who completed IVDP and entered IVMP
- Number of participants randomized
- Number of participants randomized but not dosed
- Number of participants who completed DBTP, who are ongoing and who early discontinued treatment or DBTP and associated reasons for discontinuation. Among these participants, the number of participants who entered into the subsequent periods (Safety follow period or LTE) or did not enter into the subsequent periods will also be described
- Number of participants entering into safety follow-up period, who completed safety follow-up period and who early discontinued the study and associated reason for discontinuation. Among these participants, the number of participants who completed or not the DBTP will be described
- Number of participants entering into the LTE

The number of participants in each analysis set will be also presented in the SAF set. The number of participants per country and site will also be provided using the SAF and ENR sets.

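### Efficacy is analysed by treatment received, so an error that changes a participant's arm would undo the randomised within-cohort comparison (16 v 8), with only an optional, unspecified sensitivity analysis as safeguard.

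*SAP*

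**What the plan says.** Section 4.1 defines the Safety Set (SAF) as randomised participants who received at least one dose, or part of one, of IMP. It says of this set: "Participants will be analyzed according to the treatment they received". It then makes the set the efficacy population, "The SAF will be used to analyze efficacy endpoints", and repeats the grouping rule: "For analyses performed on the SAF, PK and PD sets, the actual treatment arm will be considered". The only provision for an allocation error is: "If a treatment switch or misallocation occurred, sensitivity analyses might be performed".

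The list of analysis sets in 4.1 (Enrolled, Safety, PK, PD) contains none analysed by randomised arm. Section 6.5 and the table list in 9.2.1 place the efficacy outputs, including both the trial-product and the treatment-policy ANCOVAs, on the Safety Set. Section 6.2.1.2 compares each active group with the placebo group of its own cohort for the continuous endpoints.

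In section 6.3.1, the disposition table for the SAF includes the row "Number of participants randomized but not dosed".

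**The concern.** Randomisation makes the arms comparable only when participants are counted in the arm to which they were assigned. Grouping by actual treatment keeps that protection for as long as nobody receives another arm's treatment. Once somebody does, the contrast within that cohort is partly observational. Treatment received is the natural grouping for safety, which is this trial's primary objective. For efficacy, the usual choice is the randomised arm.

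The safeguard is weak because it leaves open both whether an analysis is done and what it would be. Section 2.1 unblinds each cohort at its interim lock, so that choice could be made with allocation known.

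The disposition row is a separate, smaller slip. A set that requires a dose cannot contain an undosed participant.

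**Working it through.** **Inputs.** Section 2.2: "for each cohort, 24 participants will be randomized" (section 2.1 says at least 24); "In a 2:1 ratio to ARGX-117 or placebo in cohort 1", and the same for options 1 and 2 of cohort 2; "In a 2:2:1:1 ratio to ARGX-117" and the placebo groups for option 3 of cohort 2. The plan gives no SD, effect size or misallocation rate, so shifts are expressed in SD units.

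**The plan's own figure (section 6.1: 48 in total, 16 per arm).**
- Total: 2 × 24 = 48.
- Each cohort at 2:1: 24 × 2/3 = 16 active and 24 × 1/3 = 8 placebo.
- Pooled placebo: 8 + 8 = 16.

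Both figures reproduce. Under option 3, cohort 2 would have 8, 8, 4 and 4, with 8 placebo after combining, so the active v placebo comparisons there would be 8 v 8.

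**Standard error of a within-cohort difference in means**, as a multiple of the SD: √(1/nA + 1/nP).
- 16 v 8: √(1/16 + 1/8) = 0.433.
- 8 v 8: √(1/8 + 1/8) = 0.500.

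**Effect of regrouping one participant** who lies k SD from the mean, assuming equal arm means.
- Placebo to active: k/(nA + 1) + k/(nP − 1).
- Active to placebo: k/(nA − 1) + k/(nP + 1), in the opposite direction.

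| Comparison | Move | k = 1 | k = 2 |
|---|---|---|---|
| 16 v 8 | placebo to active | 1/17 + 1/7 = 0.20 SD | 0.40 SD |
| 16 v 8 | active to placebo | 1/15 + 1/9 = 0.18 SD | 0.36 SD |
| 8 v 8 | either way | 1/9 + 1/7 = 0.25 SD | 0.51 SD |

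The first entry is 0.20/0.433, a little under half of one standard error.

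**The same event analysed by randomised arm.** The groups stay 16 v 8 with SE 0.433 SD. If the participant has the wrong product throughout, the true difference is diluted by at most 1/8 = 12.5% (placebo participant given active) or 1/16 = 6.25% (active participant given placebo). As treated, the groups become 17 v 7 (SE 0.449 SD) or 15 v 9 (SE 0.422 SD).

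**How likely is one such event?** The SAP gives no rate. If the chance per participant is assumed to be 0.5% to 5%, the chance of at least one in 24 is 1 − 0.995^24 = 11% to 1 − 0.95^24 = 71%. This range is illustrative and is no evidence that an error occurred.

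**Disposition row.** SAF membership requires at least part of a dose, so the count of undosed participants in the SAF is 0 whatever happens in the trial.

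**The case against.** The strongest reply is that this is an exploratory trial with safety as its primary objective, no formal hypothesis testing, and blinded participants and investigators. Randomisation and first dosing fall on the same day. An arm-changing error may never occur, and then nothing differs. All of this stands, and it limits the size of the point.

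Several stronger readings are tempting, and the SAP does not support them.
- **That any dosing or kit error breaks the comparison.** A missed, late or wrong-volume dose leaves the participant in the same arm. Only an error that changes the actual arm matters.
- **That 12.5% and 6.25% measure bias in the planned analysis.** They are one participant's share of an arm. They are also the upper limits of dilution when analysing by randomised arm, so the fix preserves randomisation but does not make an error harmless.
- **That undosed randomised participants disappear from the accounting by arm.** Section 6.3.1 also plans an enrolled-set disposition table with the number randomised. It calls that table by treatment group in one place and says enrolled-set data are shown overall in another, so the count by arm is uncertain but not shown to be lost. Listing 16.2.3.1, defined as enrolled minus SAF, would contain these participants although its title says non-randomised.
- **That version 2.0 promised an as-randomised analysis.** The modification history gives the randomised comparison as the reason for presenting results by cohort. It does not address grouping by assigned or received treatment.
- **That the plan certainly has no rule on assigning actual treatment.** A redacted block in section 4.1 stands just before the sentence on misallocation and cannot be checked.

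**Conclusion.** The point holds in a limited form. As readable, section 4.1 fixes efficacy on treatment received and leaves the remedy for a misallocation optional and undefined. In a 16 v 8 comparison, one arm-changing error in a participant 1 SD from the mean moves the estimate by about 0.18 to 0.20 SD against a standard error of 0.43 SD. In an 8 v 8 comparison it moves the estimate by about 0.25 SD against 0.50 SD. These figures assume equal arm means, 24 per cohort and a single error.

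What is at risk is the exploratory estimates and their 95% CIs. No type I error rate is involved, and without an arm-changing error the results are the same under either rule. The change should be made because it protects the randomised comparison at almost no cost, not because the planned results are known to be biased. The empty disposition row is certain but minor.

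**What to change.** 1. In section 4.1, analyse efficacy in randomised participants with at least one dose of IMP, grouped by randomised arm within cohort. Membership is the same as the SAF; only the arm label can differ.
2. Replace the optional sentence with a definite one: if a misallocation occurs, the as-treated efficacy analysis is the sensitivity analysis.
3. Keep treatment received for safety, exposure, PK, PD and ADA.
4. Move the row for participants randomised but not dosed to a table of all randomised participants by randomised arm.

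The cost is SAP wording, one population flag, relabelled efficacy titles and one relocated row. An efficacy set of all randomised participants, dosed or not, would cost more: sections 5.2 and 6.2.3 tie the efficacy period and the baseline to the first IMP administration, so undosed participants would need new rules. It is not needed here.

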### 4.2 Protocol Deviations

Protocol deviations will be classified during monthly meeting as non important or important based on their effect on the rights, safety, or wellbeing of the participants and/or the quality and integrity of the data. The final rating will be confirmed on a blinded case-by-case basis prior to database lock (DBL).

Summaries of protocol deviations will be provided by class of deviation, overall and by treatment group in the SAF.

All protocol deviations will be listed.

## 5 DATA HANDLING

### 5.1 Computing Environment

All descriptive statistical analyses will be performed using SAS statistical software (Version 9.4 or Higher), unless otherwise noted. Medical History and adverse events will be coded using MedDRA version V24.1 - Sep 2021. Prior and concomitant medications will be coded using World Health Organization (WHO) B3 WHO Drug Global - Sep 2021 version.

### 5.2 Data Conventions

In the context of this SAP, 5 periods will be considered:

**Screening period:** from the date of signing informed consent to:

- For participants who enter the IVDP: the day prior to the first IVIg administration with 23:59 added
- For participants who enter directly the IVMP: the day prior to the first IVIg administration during IVMP with 23:59 added or if the participant discontinued during the screening period the date of study termination with 23:59 added as time part
- For participants who discontinued during the screening period: the date of study termination with 23:59 added as time part

**IVIg Dependency period (IVDP):** Only defined for participants with uncertain dependency to IVIg during screening: from the first IVIg administration date with 00:00 added as part time during IVDP to the day prior to the first IVIg administration with 23:59 added in IMVP or if the participant discontinued during the IVDP period the date of study termination with 23:59 added as time part

**IVIg Monitoring period (IVMP):** from the first IVIg administration date with 00:00 added as time part during IVMP to prior to the first IMP administration (time/date) -1 minute or if the participant discontinued during the IVMP period the date of study termination with 23:59 added as time part

**Double Blind Treatment Period (DBTP):**

- For the efficacy endpoints: From the first IMP administration date/time to V14 with 23:59 added as time part or date of early treatment discontinuation visit with 23:59 added as time part
- For AE and concomitant medication: From the first IMP administration date/time to:
  - Informed consent of LTE for participants who do enter into LTE. Date of informed consent corresponds to the treatment completion date in the main study. All data on the eCRF will be considered to belong to this period
  - 23h59 the day prior to the 1st FU visit at week 4 for those participants who do not enter into LTE or date of early study discontinuation with 23:59 added as time part if participant discontinued the study before FUV1
  - Date of study discontinuation with 23:59 added for participants who early discontinued study and do not enter in the safety follow up period

**DBTP and Safety Follow-up period:** For AE, from the first IMP administration date/time to:

- Informed consent of LTE for participants who do enter into LTE. Date of informed consent corresponds to the treatment completion/discontinuation date. All data on the eCRF will be considered to belong to this period
- Study discontinuation for those participants who do not enter into LTE

Participants who entered into LTE are participants who were eligible for LTE and signed the informed consent form.

**Study Day 1 IDVP:** The day of the first IVIg administration during IDVP

**Study Day 1 IVMP:** The day of the first IVIg administration during IVMP

**Study Day 1:** The day of the first administration of ARGX-117 or placebo

**Study Day 1 FU:** The day following V14/ED visit (D113) (for participants who do not enter into the LTE)

**End of Treatment Visit:** The V14 visit (D113) for participants who completed DBTP, or the visit following IMP discontinuation for participants who discontinue IMP prior to V14 (D113) or the last IMP administration date for participants who are on-going in the DBTP at the data cut-off date .

**End of Study Visit:** The V14 visit (D113) for participants entering the LTE, or the last recorded date in the DBTP or SFU period for participants not entering the LTE.

Scheduled or Unscheduled visits which do not fall into the visit windows will be listed, but not included in tables or graphs.

- **Conversion factors:**
  - 1 month = 30.4375 days
  - 1 year = 365.25 days
  - 1 week = 7 days
  - °C = (°F - 32)/1.8
- **Additional rules**
  - Weight values recorded in pounds will be converted to kilograms using the following formula: kilograms = pounds/2.2046.
  - Height values recorded in inches will be converted to centimeters using the following formula: centimeters = inches\*2.54.
  - Duration on study (weeks) = (last visit date – informed consent date + 1) / 7.
  - Duration on treatment (weeks) = (last IMP intake date – first IMP intake date + 1) / 7.
  - Change from baseline = value at the time point – baseline value.
  - Percent relative change from baseline = [(value at the time point – baseline value) / baseline value] x 100.

### 5.3 Methods of Pooling Data

For the interim analysis 1, ARGX-117 dose regimen 1 and Placebo will be analyzed separately. For interim analysis 2 and final analysis, data from cohort 1 and cohort 2 will be presented separately, having a separate column for ARGX-117 and a column for placebo. In addition, a total column for placebo will be added, pooling participants who receive placebo either in cohort 1 or in cohort 2, forming a unique placebo arm.

### 5.4 Withdrawals, Dropouts, Loss to Follow-up

Discontinued participants who received the IMP will not be replaced.

Follow-up of participants who discontinued the IMP early will continue in the safety follow-up period until the last safety follow-up visit and the study procedures will be assessed per the schedule of activities (refer to section 9.1).

#### **Withdrawal During Treatment period:**

In case of early discontinuation during the treatment period, if possible, procedures at V14 should be conducted during an early discontinuation (ED) visit.

#### **Withdrawal During Follow-up period:**

In case of early discontinuation during the follow-up period, if possible, procedures of the last Safety Follow-up visit should be conducted during an ED visit.

### 5.5 Visit Windows

For safety, efficacy, PK, PD, immunogenicity [REDACTED], all visits (scheduled, unscheduled or early discontinuation) within a period will be mapped to an analysis visit as defined in Table 1 Table 2 and Table 3 where day 1 is defined as the first day within each period.

For GS (except for GS Net iAUC), only last analysis derived visits will apply (refer to 6.2.1.2). For GS Net iAUC, rules are described in section 6.5.1.3.

For PK and PD analyses, analysis windows for PK samples and PD samples (Free C2, total C2 and CH50) are defined in Table 4, Table 5, Table 6 and Table 7. The following considerations will have to be taken into account.

- Only the visits / timepoints defined per protocol will be considered for the analysis
- PK will be analyzed only for ARGX-117 treatment arms. Therefore, the previous or pre-previous IMP administration should refer to only active IMP administration. This implies that, in case of dose regimen 3, for which placebo administrations are planned, placebo administrations will not be taken into account.
- For PK, if the pre-dose sample is not slotted for an analysis visit, then post-dose samples should be excluded from the analysis
- For PK, in case of missing pre-dose sample, then the post-dose sample should be excluded.
- PD markers (Free C2, total C2 and CH50) are analysed for both empasiprubarb and placebo treatment arms. In case of dose regimen 3, for empasiprubarb arm, only active IMP

administration will be considered to define the window for the date of previous IMP administration. For consistency, for placebo arm of dose regimen 3, [REDACTED] will be considered for the date of previous IMP administration .

- For post-dose sample, the treatment received at the visit should be the one planned at the visit.
- The pre-dose sample should only be slotted if the treatment received at the previous IMP administration is as planned.

Per parameter and analysis window, the non missing value closest to the target day will be used in the analysis. If more than one non missing value is located at the same distance from the target day, then the one latest in time will be selected for analysis. The value latest in time will be identified using, in order of preference, the assessment time and the visit label.

For PK and PD, in case of multiple assessments within the window sample, the following rules will apply:

- For IVMP/IVDP: in case of multiple assessments per analysis visit / timepoint, the non missing value closest to the target day will be used in the analysis. Target day refers to the scheduled visit day (Table 4 and Table 5).
- During the DBTP, distinction needs to be made between pre-dose and post-dose samples:
  - For pre-dose samples, if more than one non missing value is located at the same distance from the target day, then the one latest in time will be selected for analysis (ie the closest to the IMP administration on this day)
  - For post-dose samples, in case of multiple assessments within the window sample, the closest assessment to the timepoint relatively to the start of the previous IMP administration will be selected.

Tables and listings will present the analysis visit window as defined below, not the eCRF visits. Allocations of assessments will be performed using their relative day within the period.

**Table 1 Evaluation Intervals during the screening period and IVIg dependency period**

IVIg Dosing Frequency	Protocol Scheduled Visit	Scheduled Visit Day (Relative Day during IVIg Dependency period)	Interval for Analysis Visit
	Screening		No analysis visit window
Q 2 weeks	IDV1	1	1
Q 3 weeks	IDV1	1	1
Q 4 weeks	IDV1	1	1
Q 5 weeks	IDV1	1	1
Q 2 weeks	IDV2	29	Day 2 to 23:59 on the day before IMV1

Q 3 weeks	IDV2	43	Day 2 to 23:59 on the day before IMV1
Q 4 weeks	IDV2	57	Day 2 to 23:59 on the day before IMV1
Q 5 weeks	IDV2	71	Day 2 to 23:59 on the day before IMV1

**Table 2 Evaluation Intervals during the IVIg monitoring period**

IVIg Dosing Frequency	Protocol Scheduled Visit	Scheduled Visit Day (Relative Day during IVMP)	Interval for Analysis Visit
Q 2 weeks	IMV1	1	1
Q 3 weeks	IMV1	1	1
Q 4 weeks	IMV1	1	1
Q 5 weeks	IMV1	1	1
Q 2 weeks	IMV2	15	Day 2 to Day 22
Q 3 weeks	IMV2	22	Day 2 to Day 32
Q 4 weeks	IMV2	29	Day 2 to Day 43
Q 5 weeks	IMV2	36	Day 2 to Day 53
Q 2 weeks	IMV3	29	Day 23 to end of IVMP (date/time of first IMP administration minus 1 minute) 
Q 3 weeks	IMV3	43	Day 33 to end of IVMP (date/time of first IMP administration minus 1 minute) 
Q 4 weeks	IMV3	57	Day 44 to end of IVMP (date/time of first IMP administration minus 1 minute) 
Q 5 weeks	IMV3	71	Day 54 to end of IVMP (date/time of first IMP administration minus 1 minute) 

 In case of assessment with time missing falling on date of first IMP administration, it will be allocated to IMV3.

**Table 3** Evaluation Intervals for safety and efficacy analysis during the DBTP

Category	Sub-category	Value
A	A1	10
	A2	20
B	B1	30
	B2	40
C	C1	50
	C2	60
D	D1	70
	D2	80
E	E1	90
	E2	100
F	F1	110
	F2	120
G	G1	130
	G2	140
H	H1	150
	H2	160
I	I1	170
	I2	180
J	J1	190
	J2	200
K	K1	210
	K2	220
L	L1	230
	L2	240
M	M1	250
	M2	260
N	N1	270
	N2	280
O	O1	290
	O2	300
P	P1	310
	P2	320
Q	Q1	330
	Q2	340
R	R1	350
	R2	360
S	S1	370
	S2	380
T	T1	390
	T2	400
U	U1	410
	U2	420
V	V1	430
	V2	440
W	W1	450
	W2	460
X	X1	470
	X2	480
Y	Y1	490
	Y2	500
Z	Z1	510
	Z2	520

§ 87(2)(b)

**Table 4 Visit Windows for PD samples (free C2, total C2 and CH50) during IVDP**

IVIg Dosing Frequency	Protocol Scheduled Visit	Scheduled Visit Day (Relative Day during the IDVP)	Protocol Window (days)	Timepoint	Window for sample
Q2 Weeks	IDV1	1	NA	Pre-dose	Assessment date/time before first IVIg administration
Q3 Weeks	IDV1	1	NA	Pre-dose	Assessment date/time before first IVIg administration
Q4 Weeks	IDV1	1	NA	Pre-dose	Assessment date/time before first IVIg administration
Q5 Weeks	IDV1	1	NA	Pre-dose	Assessment date/time before first IVIg administration
Q2 Weeks	IDV2	29	±7	Pre-dose	Date of previous IVIg administration + 28 days ± 7 days and performed before IVIg administration at this visit
Q3 Weeks	IDV2	43	±7	Pre-dose	Date of previous IVIg administration + 42 days ± 7 days and performed before IVIg administration at this visit
Q4 Weeks	IDV2	57	±7	Pre-dose	Date of previous IVIg administration + 56 days ± 7 days and performed before IVIg administration at this visit
Q5 Weeks	IDV2	71	±7	Pre-dose	Date of previous IVIg administration + 70 days ± 7 days and performed before IVIg administration at this visit

